### 5.3 STRATEGIES FOR RECRUITMENT AND RETENTION

#### 5.3.1 *Target Sample Size*

Recruitment into the study will be solely offered to the 19 participants who have completed the previous study GM 0017. Up to 15 participants from GM 0017 will be targeted for recruitment to this study. We expect that 12 of the 15 participants will complete the study (80%), which is providing at least 75% valid PK blood samples including Day 28 and Day 168 Vivitrol trough levels.

#### 5.3.2 *Recruitment*

All participants will be seen by a study clinician (MD or PA) for a screening evaluation and mental status examination as part of routine admission procedures at Clinilabs. Final informed consent for the study will be obtained after full medical workup is complete. The research staff knows the protocol well, and is able to explain study to the participant. Procedures for training study clinicians in the protocol and consent form include initial presentations by the Principal Investigator (PI) at weekly staff meetings, and weekly discussion of inclusion/exclusion criteria and study eligibility for each screening participant.

Study participation will only be offered to those that have successfully completed GM 0017 and therefore no advertising for recruitment outside of GM 0017 participants is required.

#### 5.3.3 *Retention*

All participants will be reimbursed as per section 7.9 for each clinic visit to compensate them for the time spent doing research assessments as well as the cost of transportation. We will maintain a close phone contact with participants to confirm each visit, and to reschedule in case of a missed visit.

## 5.4 PARTICIPANT WITHDRAWAL OR TERMINATION

### 5.4.1 *Reasons for Withdrawal or Termination*

- A participant may withdraw from the study at any time or for any reason without being obliged to divulge their reason for doing so to the investigators or clinic staff.
- A participant may be withdrawn from the study if there are unacceptable AEs, laboratory abnormalities or any other medical condition or situation including distress due to effects of any study procedure or medication.
- A participant may be withdrawn from the study if in the opinion of the treating clinician the participant's interests are best served by withdrawing from the study.
- A participant may be withdrawn from the study if the participant meets an exclusion criterion (either newly developed or not previously recognized) that precludes further study participation.

### 5.4.2 *Handling of Participant Withdrawals or Termination*

Participants, who do not receive the IP (i.e. Vivitrol), for any reason, are not considered study failures. A participant may be discontinued from the study at any time if the participant, investigator, or Sponsor determines that it is not in the best interest of the participant to continue participation. Reasons for discontinuation may include:

- Adverse event
- Withdrawal of participant
- Lost to follow-up
- Study terminated by investigator
- Pregnancy
- Clinical worsening
- Other

#### 5.4.2.1 Participant Monitoring and Removal from Study

The psychiatrist and/or therapist will assess appropriateness for continuation in the research study on a continuous basis and will remove from the trial participants with significant clinical deterioration or noncompliance of a type which could be dangerous. Criteria for removal from the study will include:

1. Clinical deterioration which cannot be managed safely in the context of outpatient treatment. This would include a participant who becomes suicidal, or a participant who goes on drug binges (including non-opiate drugs).
2. Elevation of liver enzymes  $>3$  times normal. The PI or a study physician is available 24 hours/day by phone in case of emergency.

For those who withdraw from the study may request to withdraw from data collection and have no further contact with study site. Participants shall be informed that for a period of time 30 days after their last Vivitrol injection there may a risk that opioid based medication may have a reduced affect. There is no option to remove Vivitrol from a participant.

## **5.5 PREMATURE TERMINATION OR SUSPENSION OF STUDY**

This study may be temporarily suspended or prematurely terminated if there is sufficient reasonable cause. Written notification, documenting the reason for study suspension or termination, will be provided by the suspending or terminating party to PI and Sponsor. If the study is prematurely terminated or suspended, the PI will promptly inform the NYSPI IRB, Data Safety Monitoring Panel (DSMP), FDA and will provide the reason(s) for the termination or suspension.

Circumstances that may warrant termination or suspension include, but are not limited to:

- Determination of unexpected, significant, or unacceptable risk to participants
- Insufficient compliance to protocol requirements
- Data that are not sufficiently complete and/or evaluable

Study may resume once concerns about safety, protocol compliance, data quality are addressed and satisfy the Sponsor, NYSPI IRB, DSMP and FDA.

## 6 STUDY AGENT

### 6.1 STUDY AGENT(S) AND CONTROL DESCRIPTION

#### 6.1.1 *Acquisition*

Vivitrol as manufactured by Alkermes, will be sourced from commercially available suppliers

[figure not shown]
[figure not shown]
[figure not shown]
[figure not shown]
#### 6.1.2 *Formulation, Appearance, Packaging and Labelling*

[figure not shown]
##### 6.1.2.1 Manufacturing and Sterility

Vivitrol is an FDA approved product manufactured by Alkermes. Vivitrol is a sterile IM injection and is to be used as a reference drug product in the development of the OLANI and shall be sourced from commercially available supplies.

##### 6.1.2.2 Packaging

	

1. Remove the carton from refrigeration. Prior to preparation, allow drug to reach room temperature (approximately 45 minutes).

2. To ease mixing, firmly tap the VIVITROL Microspheres vial on a hard surface, ensuring the powder moves freely. (see Figure B)

3. Remove flip-off caps from both vials. DO NOT USE IF FLIP-OFF CAPS ARE BROKEN OR MISSING.

4. Wipe the vial tops with an alcohol swab.

5. Place the 1 inch preparation needle on the syringe and withdraw 3.4 mL of the diluent from the diluent vial. Some diluent will remain in the diluent vial.

	

1. Inject the 3.4 mL of diluent into the VIVITROL Microsphere vial.

	
 
2. Mix the powder and diluent by vigorously shaking the vial for approximately 1 minute.
 
3. Ensure that the dose is thoroughly suspended prior to proceeding to Step E.
 

	
 
1. Immediately after suspension, withdraw 4.2 mL of the suspension into the syringe using the same preparation needle. (see Figure E)
 
2. Select the appropriate needle for an intramuscular injection based on patient's body habitus: 
 
a. 1.5 inch TERUMO Needle
 
b. 2 inch NEEDLE-PRO Needle
 
 
 

	
 
1. Remove the preparation needle and replace with appropriately selected administration needle for immediate use.
 
2. Peel the blister pouch of the selected administration needle open halfway. Grasp sheath using the plastic pouch. Attach the luer connection to the syringe with an easy clockwise twisting motion.
 
3. Seat the needle firmly on the needle protection device with a push and clockwise twist.
 

	
 
1. Pull the sheath away from the needle – do not twist the sheath because it could result in loosening the needle.
 
2. Prior to injecting, tap the syringe to release any air bubbles, then push gently on the plunger until 4 mL of the suspension remains in the syringe.
 
 
THE SUSPENSION IS NOW READY FOR IMMEDIATE ADMINISTRATION.

1. Administer the suspension by deep intramuscular (IM) injection into a gluteal muscle, alternating buttocks per monthly injection.
2. If blood aspirates or the needle clogs, do not inject. Change to the spare needle provided in the carton and administer into an adjacent site in the same gluteal region, again aspirating for blood before injection.
3. Inject the suspension in a smooth and continuous motion.

#### **6.1.2.3 Disposal**

Dispose of as per manufacturer's instructions.

#### ***6.1.3 Product Storage and Stability***

The entire dose kit should be stored in the refrigerator (2-8 °C, 36-46 °F). Unrefrigerated, VIVITROL Microspheres can be stored at temperatures not exceeding 25 °C (77 °F), for no more than 7 days prior to administration. Unrefrigerated Vivitrol should not be exposed to temperatures above 25 °C (77 °F). VIVITROL should not be frozen.

#### ***6.1.4 Preparation***

Refer to manufacturer's product information sheet.

#### ***6.1.5 Dosing and Administration***

Participants shall be dosed as per the schedule outlined in Table 7-1.

#### ***6.1.6 Route of Administration***

Intramuscular injection in the buttock region (gluteal muscle) as per manufacturer's product information sheet.

#### ***6.1.7 Dose Adjustments/Modifications/Delays***

Not applicable

#### ***6.1.8 Duration of Therapy***

Time in therapy: 196 days

Total anticipated study length (including recruitment): 9 months

#### ***6.1.9 Tracking of Dose***

All participants will be administered a single Vivitrol injection into the gluteal muscle as per the schedule in Table 7-1, alternating between left and right gluteal muscle as tolerated, with the exact site being recorded.

All follow up visits will check for AE's related to the IP and where appropriate any injection site reactions.

**6.1.10 Device Specific Considerations**

Not applicable.

**6.2 STUDY AGENT ACCOUNTABILITY PROCEDURES**

Vivitrol for the study shall be sourced from a commercial supplier by the PI. The PI (or delegated study personnel) will sign that they have received all IP. IP will be kept in a securely locked refrigerated cabinet under appropriate temperature conditions and a drug inventory and temperature log maintained. All unused supplies must be accounted for and destroyed with an appropriate certificate of destruction in the event it is not used.

## 7 STUDY PROCEDURES AND SCHEDULE

### 7.1 STUDY PROCEDURES/EVALUATIONS

#### 7.1.1 *Study Specific Procedures*

##### 7.1.1.1 Screening

The Screening Visit (conducted at Clinilabs) will include assessments necessary to determine study eligibility. The nature of the study and its risks and benefits will be explained to the participant by the study clinician who will also obtain a written informed consent from each potential participant prior to the administration of any study-specific procedures. The most important aspects of the protocol such as the IP administration are discussed in great detail. The study clinician (MD or PA) will perform a medical and psychiatric evaluation including a medical history and a physical examination. Medical staff or certified research assistants obtain electrocardiogram (ECG) and blood for complete blood count with differential, chemistry profile, liver function tests and pregnancy tests (if applicable). Urine is obtained for urinalysis and toxicology.

##### 7.1.1.2 Recruitment Visit

Study-trained medical professionals such as a physician or a physician assistant that has been medically trained by the study PI to consent participants to the study and provide them with all necessary medical information will discuss questions related to the study procedure and the consent form. During the Recruitment Visit (conducted at Clinilabs) a study-trained medical professional confirms that a participant meets all inclusion/exclusion criteria, is medically healthy to participate in the study. A study-trained medical professional also reviews and signs the inclusion/exclusion checklist and signs off on enrollment documentation. A procedure note for the medical chart will be included and signed verifying that a study-trained medical professional reviewed results of the evaluation and obtained informed consent. Following study enrollment, a study-trained medical professional assumes medical responsibility and arranging hospitalization for IP administration at Clinilabs followed by in-patient care at Clinilabs.

##### 7.1.1.3 Naloxone challenge test (NCT)

All participants will undergo an NCT at Clinilabs prior to IP administration. Participants will receive 0.8 mg naloxone, IM, followed by q10 minutes observation by study clinician or nurse over 30 minutes for signs and symptoms of opiate withdrawal.

Naloxone injection may cause withdrawal symptoms such as nausea, vomiting, diarrhea, stomach pain, fever, sweating, body aches, weakness, running nose, goosebumps, shivering, increased heart rate, and anxiety. Most of these effects will wear off after 20-30 minutes and treatment is usually not needed but in case of severe symptoms, participants will be offered a dose of clonidine 0.1 mg and/or clonazepam 0.5 mg. In that case, participants will be monitored for up to 6 hours until all symptoms resolve, and they can be released.

If a participant passes the NCT then they will progress to IP administration with the injection procedure (see Section 7.1.1.4).

##### 7.1.1.4 Injection procedure (initial)

Following a successful NCT, the injection of IP (Vivitrol), is to be performed as per the manufacturer's instructions. The injection will be performed at the Clinilabs site. Participants will then remain at the Clinilabs research facility for 48 hours so that intensive

portion of the blood collection can occur.

#### **7.1.1.5 Injection procedure (repeat dose)**

There are 4 instances whereby participants will be re-administered Vivitrol 28 days apart with no intensive blood monitoring scheduled following re-administration of Vivitrol and no overnight stay. These are for Vivitrol injections 2, 3, 4 and 5 as outlined in Table 7-1. In these instances, participants will be seen on an out-patient basis at Clinilabs for their re-administration of Vivitrol. Just prior to re-administration of Vivitrol, a NTX blood sample will be collected to capture the Vivitrol/naltrexone trough level. The actual time of each PK sample collection shall be recorded relative to the re-administration of Vivitrol.

There are 2 instances whereby participants are administered Vivitrol injections and then remain at the Clinilabs research facility for intensive blood collections. These instances, Vivitrol injections 1 and 6, are detailed in depth in the admissions descriptions of 7.3.3.1, 7.3.3.2, 7.3.3.3 and 7.3.3.4.

## **7.2 LABORATORY PROCEDURES/EVALUATIONS**

### ***7.2.1 Clinical Laboratory Evaluations***

Samples will be collected in accordance with Clinilab's procedures and sent for analysis to Lab Corp.

For the following test, 4.5 mL of blood will be collected in 1 x EDTA tube:

- *[FBC] Full Blood Count*

For the following tests, 5 mL of blood will be collected in 1 x SST tubes:

- *[EUC] Electrolytes, Urea, Creatinine*
- *[LFT] Liver function Tests (bilirubin, ALP, GGT, ALT, ALB, TP)*

For the following tests, a sample of urine is collected:

- *Urinalysis; LEU (Leucocytes), NIT (Nitrite), PRO (Protein), pH, BLD (Blood), SG (Specific Gravity), KET (Ketones), GLU (Glucose)*
- *[UDS] Full drug screen including buprenorphine assay.*

**Pregnancy test:** a blood test is done initially, with urine tests done monthly afterwards. A blood test will be used to confirm a positive urine result.

### ***7.2.2 Other Assays or Procedures***

#### **7.2.2.1 Naltrexone Blood Assay**

1 x 10 mL of whole blood in Na Heparin tubes (9 mL). Samples will be centrifuged for 15 min at 2,000 rpm. Plasma will then be extract and stored in suitable containers (1.5 mL Eppendorf's) for storage at -80°C for transport to WuXi laboratories under dry ice in batches for free (unconjugated) NTX and free (unconjugated) 6βN analysis.

#### ***7.2.3 Total amount of Blood to be collected***

The amount of blood drawn for the study is:

- Total LFT, EUC and FBC = 180.5 mL (18 x 9.5 mL)

- Pregnancy testing (Female participants only) = 4 mL (during the trial, a blood test will be used to confirm a positive urine result)
- Total blood samples for NTX / 6 $\beta$ N
  - 387 mL (43 x 9 mL)
- There is also the potential for further bloods to be taken on any un-scheduled visit for PK bloods (9 mL) and follow-up visit for outstanding AEs (LFT, EUC and FBC 9.5 mL) post end of trial.

The total scheduled blood collection is approximately 581.5 mL over the period of 196 days.

#### ***7.2.4 Specimen Preparation, Handling and Storage***

##### **7.2.4.1 Naltrexone PK Blood Samples**

All NTX blood samples will be collected in 1 x 10.0 mL Na Heparin tubes (9 mL) and stored in the study site refrigerator at 0-4°C until specimen preparation.

Specimen preparation will be carried out at study site within 24 hours. This will involve centrifugation of the blood sample to enable plasma separation. Plasma will be extracted and stored in suitable containers (1.5 mL Eppendorf's) and stored at -80°C. When batches of greater than 50 samples are available these can then be shipped on dry ice to WuXi Laboratories for analysis. Backup samples will remain stored at Clinilabs for the duration of the trial.

#### ***7.2.5 Specimen Shipment***

Plasma will be stored for batch shipment to WuXi Laboratories, [name] for analysis. Storage of samples at -80°C will be done at Clinilabs. Shipment of samples from Clinilabs to WuXi will be done under dry ice.

### **7.3 STUDY SCHEDULE**

#### ***7.3.1 Screening Visit***

Participant shall be screened for inclusion and exclusion criteria and overall suitability for the study.

- Obtain informed consent for screening.
- Review medical history to determine eligibility based on inclusion/exclusion criteria.
- Review medications history to determine eligibility based on inclusion/exclusion criteria.
- Perform medical examinations, including Patient Health Questionnaire (PHQ-9), Beck Depression Inventory (BDI)-II, and C-SSRS to determine eligibility based on inclusion/exclusion criteria.
- Concomitant medication review
- Collect blood for LFT, FBE and EUC.
- Collect blood for NTX and 6 $\beta$ N measurement.
- Collect blood/urine for pregnancy test in female participants.

- Self-reported substance use and UDS

### **7.3.2 *Recruitment***

At the Recruitment visit the following will take place;

- Obtain informed consent for IP administration.
- Concomitant medication review

### **7.3.3 *IP Administration (in-patient care)***

#### **7.3.3.1 Admission Day 0**

Participants will be admitted to Clinilabs where they will complete the PHQ-9, BDI-II, Substance Use assessment, concomitant medication review, AE monitoring and provide a blood/urine sample for pregnancy testing. Each participant will then undergo the NCT to confirm absence of opiate physical dependence. Participants will be scheduled to for administration of Vivitrol at Clinilabs as outlined in section 7.1.1.4. When feasible, participants will be fitted with the IV cannula to aid in the collection of blood sample for the first 48 hours. There shall be no use of heparin to keep the cannula clear as this may affect the blood analysis of NTX and 6 $\beta$ N. Processing and storage of blood samples shall be done as per section 7.2.4.1.

NTX blood samples (see section 7.2.4.1) will be collected at the following time points: baseline (before Vivitrol administration), 1 hour  $\pm$ 15 min, 2 hours  $\pm$ 15 min, 4 hours  $\pm$ 30 min, 8 hours  $\pm$ 60 min, and 12 hours  $\pm$ 60 min. The actual time of each PK sample collection shall be recorded.

Participants will also be monitored for AEs, Vital Signs and concomitant medication review.

#### **7.3.3.2 Admission Day 1**

NTX blood samples (see section 7.2.4.1) will be collected at 24 hours  $\pm$ 2 hours, 36 hours  $\pm$ 2 hours and 42 hours  $\pm$ 2 hours after Vivitrol administration. The actual time of each PK sample collection shall be recorded.

Participants will also be monitored for AEs and concomitant medication review.

#### **7.3.3.3 Admission Day 2**

NTX blood samples (see section 7.2.4.1) will be collected at 48 hours  $\pm$ 2 hours after Vivitrol administration. The actual time of each PK sample collection shall be recorded.

Participants will also be monitored for AEs and concomitant medication review.

Participants will then be discharged and provided with a timetable for their follow-up visits, which will be carried out at Clinilabs.

#### **7.3.3.4 Admission Day 140 to 142**

NTX blood samples (see section 7.2.4.1) will be collected at 140 days  $\pm$  1 day sample prior to Vivitrol re-administration. Participants will then be administered their sixth and final Vivitrol IM injection on Day 140 and the time recorded. NTX blood samples will be collected at 140 days +1 hr  $\pm$ 15 min, 140 days +2 hr  $\pm$ 15 min, 140 days +4 hr  $\pm$ 30 min, 140 days +8 hr  $\pm$  60 min, 140 days +12 hr  $\pm$ 60 min, 141 days  $\pm$  2 hr, 141.5 days  $\pm$ 2 hr, 141.75 days  $\pm$ 2 hr, 142 days  $\pm$ 2 hr under in-patient care. The actual time of each PK sample collection shall be recorded. Participants will then be discharged and provided with a timetable for their follow-

up visits, which will be carried out at Clinilabs.

Participants will also be monitored for AEs, concomitant medication review, Substance Use: Self report & UDS. Where applicable, a pregnancy test will also be conducted.

#### **7.3.3.5 Vivitrol re-administration Day 28, 56, 84 & 112 ( $\pm 1$ day)**

There will be no intensive blood monitoring scheduled after administration of the 2nd, 3rd, 4th and 5th dose of Vivitrol as outlined in Table 7-1. In this instance, participants will be seen on an out-patient basis at Clinilabs for their re-administration of Vivitrol. Just prior to re-administration of Vivitrol, blood samples will be taken for: LFT, EUC & FBE; and NTX PK analysis to capture the Vivitrol trough level. The actual time of each PK sample collection shall be recorded relative to the re-administration of Vivitrol.

Participants will also be monitored for the following: AEs, PHQ-9, BDI-II, CSSRS, concomitant medication review, Vital signs, substance Use (Self report) and UDS. Where applicable a pregnancy test will also be conducted.

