#### ***7.3.4 Follow-Up***

Participants will be instructed to attend the Clinilabs facility to continue study procedures as per the protocol time points outlined in Table 7-1. There are allowable variations in actual day of collection as long as the variation is recorded. At these time points, PK blood will be collected along with an injection Site assessment where applicable, PHQ-9 & BDI-II, concomitant medication review and AE monitoring.

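### The liver test behind the removal rule is drawn just before injections 2 to 5 with no result required first, so injection 2 may rest on the screening test alone

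*Combined protocol and SAP*

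**What the plan says.** Section 5.4.2.1 lists "Elevation of liver enzymes" above three times normal among the criteria for which participants will be removed. The same section states: "There is no option to remove Vivitrol from a participant".

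For injections 2 to 5, section 7.3.3.5 fixes the time of the test: "Just prior to re-administration of Vivitrol, blood samples will be taken for: LFT, EUC & FBE". Section 7.2.1 says clinical samples are "sent for analysis to Lab Corp" and gives no turnaround time and no same-day or on-site test.

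The other sections that describe repeat dosing add no LFT step:

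- Section 7.1.1.5 names only the drug level: "Just prior to re-administration of Vivitrol, a NTX blood sample will be collected to capture the Vivitrol/naltrexone trough level".
- Section 7.3.3.4, for injection 6, gives the pre-dose naltrexone sample and then: "Participants will also be monitored for AEs, concomitant medication review, Substance Use: Self report & UDS". No LFT is listed. Table 7-1 marks one for the Day 140 to 142 admission without placing it before or after the injection.
- Section 6.1.7, "Dose Adjustments/Modifications/Delays", is marked as not applicable.
- Section 7.3.4 describes the visits between injections: "PK blood will be collected along with an injection Site assessment where applicable, PHQ-9 & BDI-II, concomitant medication review and AE monitoring". No LFT is listed, and Table 7-1, as read from the public copy, marks none on Days 3 to 24.

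**The concern.** A removal rule protects a participant only if the result that triggers it is known before the next irreversible step. Here the test is drawn minutes before that step and sent elsewhere. A participant whose enzymes already exceed the limit could then receive that day's 380 mg with every section followed.

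The case at issue is a rise without symptoms. A symptomatic participant should be caught by adverse event monitoring at the injection visit. Section 2.3.1 (item 4) reports transient, asymptomatic transaminase rises with this product, and sections 3.2 and 4.2.2 make hepatic effects an adverse event of special interest. Section 2.3.2 acknowledges that these volunteers have no known benefit to set against an avoidable exposure.

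**Working it through.** The plan states no figure for this, so the check sets the LFT draws against the injections.

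**Inputs**
- Injections on Days 0, 28, 56, 84, 112 and 140, each 380 mg (study schematic, section 4.1).
- Scheduled LFTs in Table 7-1: screening, Days 28, 56, 84 and 112, the Day 140 to 142 admission, and Day 196, which makes 7.
- Windows: ±1 day for these visits, ±2 days for injections (Table 7-1, footnote 7).
- Assumption: the result does not return within the dosing visit.
- Assumption: screening takes place 7 to 30 days before Day 0. The protocol sets no limit.

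**Latest result in hand at each repeat injection**

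| Injection | Day | Latest result in hand | Nominal age (days) |
|---|---|---|---|
| 2 | 28 | Screening | 28 + 7 = 35 to 28 + 30 = 58 |
| 3 | 56 | Day 28 | 56 − 28 = 28 |
| 4 | 84 | Day 56 | 84 − 56 = 28 |
| 5 | 112 | Day 84 | 112 − 84 = 28 |
| 6 | 140 | Day 112 | 140 − 112 = 28 |

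For injections 3 to 6, draw and injection fall at the same visit, so the windows of two visits combine. The age is 28 ± 2 = 26 to 30 days with ±1 day, or 28 ± 4 = 24 to 32 days with ±2 days.

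**Extra injections.** A rise that begins after any of injections 1 to 5 is first sampled at the next dosing visit. If the result comes later, one further injection is given before the rule can act. If it is same-day and looked at, none is. A rise after injection 6 meets no further dose.

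**With an LFT on Day 24.** Injection 2 would rest on an on-treatment result 28 − 24 = 4 days old. If the Day 28 LFT is kept, injection 3 still rests on a 28-day-old result. If it is moved to Day 24 instead, that becomes 56 − 24 = 32 days, so adding is better than moving.

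**Blood.** 5 / 581.5 = 0.86% of the total in section 7.2.3. The components listed there sum to 180.5 + 4 + 387 = 571.5 mL, and 5 / 571.5 = 0.87%, so the discrepancy makes no practical difference.

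**A possible contrary sign.** Section 7.2.3 budgets 18 safety draws against the 7 marked, leaving 18 − 7 = 11 unexplained. The line is itself inconsistent, since 18 × 9.5 = 171 mL while the stated 180.5 mL is 19 × 9.5. It cannot settle whether a Day 24 LFT was intended.

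**The case against.** The strongest reply is that the protocol already obliges staff to act. Section 5.4.2.1 calls for continuation to be assessed continuously and says participants who meet the criteria will be removed. Section 8.6.2 adds weekly safety monitoring by the investigator's team. Over a 28-day interval these duties should ensure that the previous result is seen and acted on. This stands. A reader might infer that no LFT result at all needs to be looked at before dosing, but the documents do not support that. Neither duty, however, can supply a result that has not come back, and before injection 2 there is no earlier on-treatment result.

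Other points also stand in part:

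- Turnaround is unstated, and the site's own procedures may deliver same-day results. The lag is conditional on that.
- A reader might take section 6.1.7 to rule out any wait for a result. Footnote 7 of Table 7-1 allows injection up to two days late, so there is some room, although nothing says to use it.
- A reader might count two of six doses as given without an on-treatment result. Dose 1 precedes any such result in every trial, so the informative count is one dose, 380 mg.
- Some marks in Table 7-1 look doubtful. The Day 3 to 24 row shows a pregnancy test but no adverse event monitoring, which section 7.3.4 requires. With the 18-draw budget, this leaves open that a Day 24 LFT is already intended.
- A reader might infer that stops for hypersensitivity or symptomatic hepatitis are missing. They are current text in section 2.3.1 (items 8 and 4), so no change is proposed there.
- Entry excludes ALT or AST above three times the upper limit, and the product is approved. The documents give no rate from which to project harm.

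**Conclusion.** The point holds as a cheap safety improvement. If LFT results are not same-day, following the schedule exactly gives injection 2 on the screening LFT alone, and gives injections 3 to 6 on a result about 28 days old. The effect is at most one extra, non-removable 380 mg injection per affected participant, and zero if results are same-day.

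The conclusion rests on the unstated turnaround and on Table 7-1 having no LFT on Days 3 to 24. It does not extend to a forecast of how many participants would be affected, or to any bias in the pharmacokinetic results.

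**What to change.** 1. In Table 7-1 and section 7.3.4, add an LFT to the existing Day 24 blood-draw visit and keep the Day 28 LFT. Require the Day 24 result to be reviewed against the rule of three times normal before the Day 28 injection.
2. In sections 7.3.3.4 and 7.3.3.5, add: *Before each of injections 3 to 6, a study clinician checks the latest available LFT result. The injection is held if the liver-enzyme criterion in section 5.4.2.1 is met.* Amend section 6.1.7 to refer to this hold and to the Day 24 review.

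If the 18 draws in section 7.2.3 already include Day 24, only the review step is needed.

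The cost is one 5 mL tube per participant at a visit that already draws blood (15 tubes for up to 15 participants, about 0.9% of the stated volume each), plus a short check. Item 2 mostly writes down what staff should already do.

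The limit is that a lag of up to one dose remains for injections 3 to 6 unless results are same-day. Removing it would need on-site testing, which the protocol does not describe, or up to 4 extra visits per participant (4 × 15 = 60 visits; 60 × $50 = $3,000 at the visit rate in section 7.9, before transport). That is left to the sponsor.
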